8.1.2 Serious Adverse Events

An AE or suspected adverse reaction is considered a SAE if, in the view of either the Site PI or Sponsor, it results in any of the following outcomes:

Death,

a life-threatening adverse AE¹,

inpatient hospitalization or prolongation of existing hospitalization,

a persistent or significant incapacity or substantial disruption of the ability to conduct normal life functions, or

a congenital anomaly/birth defect,

Important medical events that may not result in death, be life-threatening, or require hospitalizations may be considered serious when, based upon appropriate medical judgment they may jeopardize the patient or subject and may require medical or surgical intervention to prevent one of the outcomes listed in this definition. Examples of such medical events include allergic bronchospasm requiring intensive treatment in an emergency room or at home, skin ulcers (open sores) at the injection site, blood dyscrasias or convulsions that do not result in inpatient hospitalization, or the development of drug dependency or drug abuse.

¹ An AE is considered “life-threatening” if, in the view of either the Site PI or Sponsor, its occurrence places the patient or subject at immediate risk of death. It does not include an AE that, had it occurred in a more severe form, might have caused death.

SAEs will be:

Assessed for severity and relationship to study product and alternate etiology (if not related to study product) by a licensed study physician listed on Form FDA 1572 or by the Site PI or Sub-Investigator.

Recorded on the appropriate SAE DCF and eCRF.

Followed through resolution by a licensed study physician (for Investigation New Drug (IND) studies, a physician listed on Form FDA 1572 as the Site PI or Sub-Investigator).

Reviewed and evaluated by DMID, an Independent Safety Monitor (ISM) (as deemed necessary), the SMC (periodic review unless related), and the IRB/IEC.

8.1.3 Adverse Events of Special Interest

In addition to SAEs, the following adverse events of special interest (AESIs) should be promptly reported to the Sponsor even if the nature of the adverse event is deemed non-serious according to the usual regulatory criteria.

Intravenous Infusion Intolerance

Events that, in the opinion of the Investigator, may represent intolerance of the IV infusion of the study drug must be recorded as AEs on the eCRF. In general, these events would be temporally associated with the IV infusion of the Sponsor’s study drug.

Phototoxicity

Due to preliminary results from a nonclinical phototoxicity study in rats, subjects should be advised to avoid sun exposure without adequate protection. Site PIs should report any AE potentially related to phototoxicity to the Sponsor.

Neuropathy and Tremors

In a rezafungin 3-month toxicity study in monkeys, there were observations of tremors, and histology consistent with axonal degeneration (potentially consistent with clinical presentation of neuropathy) first appearing at Week 6 of dosing and at 11-fold the exposure for the rezafungin for Injection dose in this study. Ataxia, axonal neuropathy, hypoesthesia, paresthesia, peripheral

motor neuropathy, peripheral neuropathy, peripheral sensory neuropathies, peripheral sensorimotor neuropathy, polyneuropathy, toxic neuropathy, and tremors should be considered AESIs. Site PIs should report any AE potentially related to neuropathy to the Sponsor.

Skin Ulcers

Skin ulcerations of any grade at study drug injection sites will be of special interest. Site PIs should report any skin ulcerations at injection sites to the Sponsor within 24 hours of site awareness. Sponsor will report skin ulcerations at injection sites to the FDA as per Expedited Reporting guidelines. Any skin ulcerations at site(s) of injection will be assessed daily while inpatient; following discharge from the unit, the Site PI will determine the frequency of monitoring until resolution or stabilization. The status of skin ulcerations will be followed until resolution.

8.2 Specification of Safety Parameters

Safety will be assessed by the frequency and severity of AEs following administration of rezafungin.

8.2.1 Injection Site Reactogenicity

The local injection site(s) will be assessed for reactogenicity with respect to symptoms. All Skin reactions at the injection site will also be measured and photographed, according to the MOP for this study. See [Appendix B](#) and [Section 7.1.4](#) for additional information.

8.2.2 New-Onset Chronic Medical Conditions

New-Onset Chronic Medical Conditions are defined as any new International Class of Diseases, Tenth Revision diagnosis that is applied to the subject during this trial, after receipt of the study agent, that is expected to continue for at least 3 months and requires continued health care intervention.

8.2.3 Dose Escalation Criteria

Dose escalation to each successive cohort of subjects will occur if none of the predefined dose escalation halting criterion is met (for all subjects through Day 30 [SAD] or Day 30 [MAD]). The SDCC will provide notification to the PI upon analysis of data for the cohort (for all subjects through Day 30 [SAD] or Day 30 [MAD]) for halting criteria as described in [Section 8.7 Study](#)

Design, Objectives and Endpoints or Outcome Measures, Dose Escalation. If any of the criterion for dose escalation is met, or, at the discretion of the PI or DMID Medical Monitor, the study enrollment and dosing will be stopped until the SMC reviews the data and provides its recommendations. There will be a scheduled SMC data review meeting prior to start of Part 2 (MAD).

8.3 Reporting Procedures

8.3.1 Reporting Serious Adverse Events

Any AE that meets a protocol-defined serious criterion must be submitted immediately (within 24 hours of site awareness) on an SAE form to the DMID Pharmacovigilance Group, at the following address:

DMID Pharmacovigilance Group

Clinical Research Operations and Management Support (CROMS)

[name]

[name]

SAE Hot Line: [name] (US) or [name] (outside US)

SAE [contact] (US) or [name] (outside US)

SAE Email Address: [contact]

In addition to the SAE form, select SAE data fields must also be entered into Advantage EDC. Please see the protocol-specific MOP for details regarding this procedure.

Other supporting documentation of the event may be requested by the DMID Pharmacovigilance Group and should be provided as soon as possible.

8.4 Type and Duration of Follow-Up of Subjects after Adverts Events

The site will send a copy of the SAE report(s) to the ISM (as deemed necessary) when they are provided to the DMID Pharmacovigilance Group. The DMID Medical Monitor and DMID Clinical Project Manager will be notified of the SAE by the DMID Pharmacovigilance Group. The DMID Medical Monitor will review and assess the SAE for regulatory reporting and potential impact on study subject safety and protocol conduct.

At any time after completion of the study, if the site principal investigator or appropriate sub-investigator becomes aware of an SAE that is suspected to be related to study product, the site PI or appropriate sub-investigator will report the event to the DMID Pharmacovigilance Group.

8.4.1 Regulatory Reporting for Studies Conducted Under DMID-Sponsored IND

Following notification from the Site PI, DMID, the IND sponsor, will report any suspected adverse reaction that is both serious and unexpected. DMID will report an AE as a suspected adverse reaction only if there is evidence to suggest a causal relationship between the study drug and the AE. DMID will notify FDA and all participating PI's (i.e., all PI's to whom the Sponsor is providing drug under its IND or under the PI's IND[s]) in an IND safety report of potential serious risks from clinical trials or any other source, as soon as possible, but in no case later than 15 calendar days after the Sponsor determines that the information qualifies for reporting as specified in 21 CFR Part 312.32. DMID will also notify FDA of any unexpected fatal or life-threatening suspected adverse reaction as soon as possible, but in no case later than 7 calendar days after the Sponsor's initial receipt of the information. Relevant FU information to an IND safety report will be submitted as soon as the information is available. Upon request from FDA, DMID will submit to FDA any additional data or information that the agency deems necessary, as soon as possible, but in no case later than 15 calendar days after receiving the request.

All serious events designated as "not related" to study drug will be reported to the FDA at least annually in a summary format.

8.4.2 Reporting of Pregnancy

A Notification of Pregnancy form will be completed for any female study subject or for any female partner of a male study subject who becomes pregnant following their exposure to study product (Day 1) through 4 months (120 days) after the last dose of study product is administered. The site will discuss pregnancy reporting with subjects at the Final Study visit with instructions and provide contact information in case pregnancy occurs. The pregnant subject will be followed by monthly telephone calls until 2 months after the birth of the baby or until the end of the pregnancy (in case pregnancy is terminated) at which time the Pregnancy Outcome form will be completed. Infants born to these study subjects will also be monitored for SAEs for up to 2 months after birth (information regarding SAEs will be captured on the Pregnancy Outcome form and the SAE form). If an SAE occurs during the pregnancy, the SAE will be reported on the appropriate SAE form and provided to DMID pharmacovigilance. Pregnancy Outcome forms will be used to collect, but not be limited to, data on the following information, should it be

identified during the monthly telephone calls, at the end of the pregnancy, or at the follow-up telephone call at 2 months after birth of the baby:

1. Prior maternal history including congenital abnormalities or pregnancy complications;
2. Estimated date of conception;
3. Estimated and actual date of delivery or pregnancy termination;
4. Mode of delivery;
5. Maternal complications;
6. Neonatal complications (i.e. lethal or nonlethal congenital abnormality).

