Echinocandins are typically well tolerated (Eraxis [anidulafungin] Prescribing information, 2013; Mycamine [micafungin sodium] Prescribing Information, 2013; Cancidas [caspofungin acetate] Prescribing Information, 2014). Potential drug class effects include risk of abnormal liver function tests, hepatitis, and hepatic failure. General and administration site events (infusion related reactions, peripheral edema, rigors, infusion site inflammation, and pyrexia) have been reported for echinocandins (Eraxis [anidulafungin] Prescribing Information, 2013; Mycamine [micafungin sodium] Prescribing Information, 2013; Cancidas [caspofungin acetate] Prescribing Information, 2014). Possible histamine-mediated symptoms have been reported in patients who received rapid infusions of echinocandins, including rash, urticarial, flushing, pruritus, dyspnea, hypotension, facial swelling, and vasodilation. Anaphylactic-like reactions have been reported with micafungin (Mycamine [micafungin sodium] Prescribing Information, 2013).

Due to preliminary results from a nonclinical phototoxicity study in rats (positive response to *in vitro* UV absorption), subjects should be advised to avoid sun exposure and any other type of

ultraviolet radiation (including tanning beds) without adequate protection. Investigators should report any AE potentially related to phototoxicity to the Sponsor.

Based on a fertility study in male rats, there is the potential risk for decreased sperm motility, increased incidences of abnormal sperm morphology, and testicular seminiferous tubular epithelial degeneration. These findings were noted at 2.5-fold the exposure expected at the highest dose in this study. The risk to humans is unknown, thus the male contraception requirements in inclusion criteria (see numbers 4 and 5 in [Section 5.1.1](#)) prohibit unprotected sexual intercourse and sperm donation within the study period and for 90 days thereafter (a total of 120 days from the last dose of study drug). This risk will be included in the ICF.

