5.1 Eligibility Criteria

5.1.1 Subject Inclusion Criteria

Subjects are eligible to enroll in this trial if they meet all the following criteria:

- 1) Males and females aged 18 to 45 years, inclusive.
- 2) Willing and able to provide written informed consent and authorization for use of protected health information;
- 3) Willing and able to comply with protocol requirements, instructions, and protocol-stated restrictions (including confinement to the CRU) and is likely to complete the study as planned;
- 4) Males must be vasectomized or agree to use barrier contraception (condom with spermicide) from first dose of study drug until at least 18 weeks following the last dose of study drug.
- 5) Males must agree to refrain from sperm donation from first dose of IP through at least 18 weeks after last dose of investigational product (IP).

6) Females are eligible if they are of non-childbearing potential³ or if they use a highly effective⁴ method of contraception for 30 days prior to dosing and for a minimum of 30 days after dosing;

³Non-childbearing potential is defined as: Pre-menopausal with documentation of irreversible surgical sterilization (i.e., hysterectomy, bilateral oophorectomy, or bilateral salpingectomy (but not tubal ligation alone); or, Post-menopausal defined as amenorrhea for at least 12 months following cessation of all exogenous hormonal treatments and with FSH levels ≥ 40 mIU/mL at Screening.

⁴A highly effective contraceptive method is, defined by <1% failure rate that is not affected by user adherence, include surgical sterilization and long-acting reversible contraception (LARC). LARC comes in three forms: progestin-releasing subdermal implants (Nexplanon and Implanon [Merck]); copper intrauterine devices (IUD) (ParaGard [Teva]); and levonorgestrel-releasing IUDs (Mirena [Bayer], Skyla [Bayer], and Liletta [Allergan/Medicines360]. Subjects must use one of these three methods.

7) Subject is in good health as deemed by the Investigator.¹⁻²

¹Good health is defined by the absence of any medical condition described in the exclusion criteria in a subject who undergoes a medical history, with a normal complete physical examination including resting vital signs (heart rate of 51-60 bpm allowed, per PI discretion), and screening safety laboratory testing.

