6.4.10 Day 30 (± 1 Day) – Follow-Up – Final Study Visit

- Obtain resting vital signs after being at rest for at least 5 minutes.
- 12-lead ECG after at least 5 minutes in the supine position (triplicate readings, at least 1 minute apart within a 15-minute period).
- Perform targeted PE.
- Obtain weight, calculate BMI.
- Obtain blood for hematology/coagulation/chemistry and urine for urinalysis.
- Perform serum pregnancy test (females of childbearing potential only).
- Obtain PK blood sample. No PK blood samples collected in Cohort 1.
- Assess reactogenicity at SC injection site(s) (see [Section 7.1.3](#) and MOP for this study).
- Assess AEs.
- Review Memory Aid.
- Review and record any concomitant medications and non-pharmacologic treatments/procedures since admission to the CRU.
- Review post-study instructions (contraceptive use, pregnancy reporting).

6.5 Part 2 (Cohorts 7 through 10)**6.5.1 Days 1, 8, and 15 – Inpatient CRU**

Study drug or placebo will be administered via SC injection in the morning on Days 1, 8, and 15. Subjects will be inpatients in the CRU and will undergo the following procedures, which are listed in the Schedule of Study Procedures and Evaluations ([Appendix A](#)) and detailed in Clinical Evaluations ([Section 7](#)):

- Randomize the subject (Day 1 only).
- Review inclusion criteria numbers 2-7 and 10-11, and exclusion criteria numbers 2-4 and 8-18 (from [Section 5.1.2](#)) to ensure the subject remains eligible for dosing (Days 8 and 15 only).
- Obtain resting vital signs before study drug dosing (within 60 minutes of study drug dosing for Day 1). This is to be documented as the Baseline prior to dosing on Day 1.
- Perform targeted PE.
- Obtain a 12-lead ECG before study drug dosing (Day 1 only) after at least 5 minutes in the supine position (triplicate readings, at least 1 minute apart within a 15-minute period) and within 60 minutes before study drug dosing.
- Baseline (Day 1) and pre-dose (Days 8 and 15) skin assessment at SC injection site area(s) prior to study drug dosing (see [Section 7.1.3](#) and MOP for this study).
- Administer study drug via SC injection in the abdomen at a slow, steady pace.
- Obtain vital signs at 15 minutes (± 5 min), 1 hour (± 10 min), and 2 hours (± 10 min) after dosing, after resting in a supine or semi-supine position for at least 5 minutes.

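### Male contraception is set at 18 weeks (126 days) after the last dose, but the risk section describes the same criteria as 120 days, and partner-pregnancy notification also ends at 120 days

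*Protocol*

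**What the plan says.** Three places in the protocol bear on this.

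- **Section 5.1.1, criteria 4 and 5.** Men who are not vasectomized must use a condom with spermicide "from first dose of study drug until at least 18 weeks following the last dose of study drug". All men must refrain from donating sperm "from first dose of IP through at least 18 weeks after last dose of investigational product (IP". The screen-failure table shell in the SAP (Table 4) repeats 18 weeks for the contraception criterion.
- **Section 2.3.1.** After describing sperm and testicular findings in male rats, the text refers to "the male contraception requirements in inclusion criteria (see numbers 4 and 5 in" Section 5.1.1 and says that they apply "within the study period and for 90 days thereafter (a total of 120 days from the last dose of study drug".
- **Section 8.4.2.** A Notification of Pregnancy form is completed "for any female study subject or for any female partner of a male study subject who becomes pregnant" from Day 1 "through 4 months (120 days) after the last dose of study product is administered".

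**The concern.** Section 2.3.1 does not set a rule of its own. It reports what criteria 4 and 5 require, and the length it reports is not the length in those criteria. Section 8.4.2 uses the same 120 days as Section 2.3.1, so the notification period for partners ends before the contraception period set by the criteria.

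The restriction exists because reduced sperm motility, abnormal sperm morphology and seminiferous tubular degeneration were seen in rats at 2.5 times the exposure expected at the highest dose in the study, and Section 2.3.1 calls the human risk unknown. If contraception failed late in the required period, the partner's pregnancy could fall where no form is required. The monthly calls and the outcome form described in Section 8.4.2 would then not be triggered.

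**Working it through.** **Inputs**

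- Male contraception and sperm-donation period: at least 18 weeks after the last dose (Section 5.1.1, criteria 4 and 5).
- Period as described in the risk section: study period plus 90 days, stated total 120 days (Section 2.3.1).
- Notification window: 120 days after the last dose (Section 8.4.2).
- Last dose and final visit: Part 1, Day 1 and Day 30; Part 2, Day 15 and Day 45; Part 3, Day 22 and Day 52 (Section 3.1.1; Sections 6.4.10, 6.5.9 and 6.6.9). The final visits have a window of ±1 day.
- Female contraception after dosing: at least 30 days (Section 5.1.1, criterion 6).

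**Step 1: reproduce the 120 days in Section 2.3.1.** Days after last dose = (final visit day - last dose day) + 90.

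| Part | Calculation | Days | With ±1 day visit |
|---|---|---|---|
| 1 (SAD) | 30 - 1 + 90 | 119 | 118 to 120 |
| 2 (MAD) | 45 - 15 + 90 | 120 | 119 to 121 |
| 3 (BA) | 52 - 22 + 90 | 120 | 119 to 121 |

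The stated 120 follows from the visit schedule, to within the visit window. It comes from a rule of follow-up plus 90 days, and is not a rounding of 18 weeks. Even the largest value, 121, is 126 - 121 = 5 days short of the criteria.

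**Step 2: length set by the criteria.** 18 x 7 = 126 days.

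**Step 3: difference.** 126 - 120 = 6 days, that is days 121 to 126 after the last dose. This is a minimum, because both criteria say at least 18 weeks.

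**Step 4: does reading the window as calendar months close the gap?** Section 8.4.2 equates four months with 120 days. If calendar months were used instead, the shortest run in a non-leap year is February to May, 28 + 31 + 30 + 31 = 120, and the longest is, for example, July to October, 31 + 31 + 30 + 31 = 123. The gap would be 126 - 123 = 3 to 126 - 120 = 6 days, so it remains.

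**Step 5: who is affected.** For female subjects the notification window outlasts the minimum contraception period by 120 - 30 = 90 days, so there is no gap. The gap concerns only female partners of male subjects. Vasectomized men are exempt from the barrier requirement but not from the sperm-donation restriction.

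**The case against.** The best defence is that the text used in practice is consistent. Footnote p to each schedule in Appendix A sends contraception and sperm-donation counselling to Section 5.1, which holds the 18-week figure, and Section 6.2 does the same for sperm donation at screening. A man who follows 18 weeks also satisfies 120 days, so the mismatch leaves no one less protected. Notification and contraception are also different things, and nothing in the protocol says their periods must be equal: for women they differ by 90 days.

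Much of this stands, and it rules out some stronger readings.

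- **A reader might infer that subjects are told two durations.** The documents do not show this. Section 2.3.1 says that the risk will go into the consent form, not that the 120 days will. The consent form is not available for this review, and the final-visit items on contraceptive use and pregnancy reporting state no duration.
- **A reader might infer that harm from a pregnancy on days 121 to 126 would go unrecorded.** Section 8.4.2 says when a form is required and does not bar later reports. A birth defect is a serious outcome under Section 8.1.2, and Section 8.4 asks for a serious event suspected to be related to be reported at any time after the study, once the site is aware of it. An uncomplicated pregnancy is not covered by that route.
- **A reader might infer a material safety consequence in this trial.** The 2.5-fold margin is against the highest planned dose. The SAP Preface records that the study was terminated on 27APR2020 with no one enrolled above 10 mg. Table 1 of the protocol planned 3 + 6 = 9 active subjects in those two cohorts, and not all need have been men to whom the barrier requirement applied. A six-day edge is also narrow when the date of conception is itself estimated.

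The defence does not remove the mismatch between Sections 2.3.1 and 5.1.1: one cites the other by criterion number and gives a different length. Nor does the comparison with women help. Their notification window is longer than their contraception period, while for partners of men it is shorter.

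**Conclusion.** The point holds as a minor internal inconsistency. Section 2.3.1 understates by 6 days a restriction that it cites by number, and Section 8.4.2 leaves the same 6 days (121 to 126 after the last dose) in which a partner's pregnancy falls within the contraception period set by the criteria but needs no notification form. The size rests on taking a week as 7 days and on the 120 days stated in both sections; under calendar months the notification gap would be 3 to 6 days. It applies to female partners of male subjects only. No endpoint, analysis population or analysis is affected. With the trial closed, the practical value lies in correcting the record and in any reuse of this text. The documents do not show which of the two durations was intended.

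**What to change.** Reconcile Sections 2.3.1, 5.1.1 and 8.4.2 to one duration in one unit, so that the male contraception and sperm-donation period and the partner-pregnancy notification period agree. Check that the consent form and the final-visit instructions (Sections 6.4.10, 6.5.9 and 6.6.9) give the same figure, and align the SAP Table 4 shell if the criterion wording changes. Which duration is right is a clinical decision for the sponsor, and none is proposed here. The cost is a wording change in one or more of these sections, plus the consent form if it proves to differ. No new data item or analysis is needed.
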